## **6. Interventions**

All patients undergo standardized general anesthesia and perioperative management as detailed below.

### **6.1 General Anesthesia Regimen**

Monitoring includes ECG, non-invasive blood pressure, pulse oximetry, and end-tidal CO2. Induction is achieved with fentanyl 2 µg/kg IV, propofol 2 mg/kg IV, and atracurium 0.5 mg/kg IV to facilitate tracheal intubation. Anesthesia is maintained with isoflurane 1–1.5% in an oxygen-air mixture (FiO2 0.5) and atracurium 0.1 mg/kg IV every 30 minutes. Ventilation is adjusted to maintain end-tidal CO2 between 30–35 mmHg. Hypotension is treated with crystalloids (0.9% saline and/or Ringer's acetate) and incremental ephedrine 5 mg doses as needed. At the end of surgery, neuromuscular

blockade is reversed with neostigmine 0.05 mg/kg and atropine 0.02 mg/kg IV and patients are extubated after full recovery.

## 6.2 Study Arms

### 6.2.1 PENG Block Group

After induction of general anesthesia and before surgical incision, patients in the PENG group are placed supine. A low-frequency curvilinear ultrasound probe (2–5 MHz) is positioned transversely over the anterior inferior iliac spine and rotated approximately 45° counter-clockwise along the pubic ramus. Key sonoanatomy includes the iliopubic eminence, iliopsoas muscle/tendon, and femoral nerve and vessels. A 22-G, 50 mm nerve block needle is inserted in-plane from lateral to medial to reach the fascial plane between the iliopsoas fascia and the pubic ramus, under the iliopsoas tendon. After negative aspiration and a 1 mL saline test injection, 30 mL of local anesthetic mixture (29 mL 0.25% bupivacaine plus 1 mL containing 4 mg dexamethasone) is injected with visualization of appropriate spread.

### 6.2.2 Anterior Quadratus Lumborum Block (AQLB) Group

After induction of general anesthesia, patients assigned to the AQLB group are positioned in the lateral decubitus position with the operative side up. A low-frequency curvilinear ultrasound probe is placed horizontally above the iliac crest to visualize the transverse process, psoas major, erector spinae, and quadratus lumborum muscles. A 22-G, 50 mm needle is advanced in-plane from posterior to anterior into the fascial plane between quadratus lumborum and psoas major. Following hydro-localization with 1 mL

saline, 30 mL of 0.25% bupivacaine with 4 mg dexamethasone (29 mL + 1 mL) is injected in this plane.

#### **6.2.3 Control Group**

Patients in the Control group do not receive a regional nerve or fascial plane block. Analgesia is based on systemic opioids only: intraoperative fentanyl and postoperative morphine as described below. A sham dressing may be applied to mimic a block site and maintain blinding.

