### **6.4 Postoperative Management**

In the post-anesthesia care unit (PACU), patients are monitored for 2 hours. NRS scores at rest and during movement, mean arterial pressure, and heart rate are recorded on arrival. On the ward, patients receive paracetamol 500 mg IV every 6 hours. Rescue analgesia consists of morphine 0.05 mg/kg IV bolus when NRS  $\geq 4$  at rest or during movement, with a maximum dose of 0.3 mg/kg in 24 hours. Ondansetron 0.1 mg/kg IV is administered for moderate or severe postoperative nausea/vomiting.

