## **7. Outcomes and Assessments**

### **7.1 Primary Outcome**

The primary outcome is total morphine consumption (mg) in the first 24 postoperative hours, calculated as the cumulative dose of intravenous morphine administered in the PACU and on the ward up to 24 hours after surgery.

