### **7.2 Secondary Outcomes**

To compare intraoperative fentanyl consumption between the three groups.

To compare time to first rescue analgesia postoperatively.

To compare Numeric Pain Rating Scale (NRS) scores at rest and during passive 90° hip flexion at predefined postoperative time points (30 min, 2, 4, 6, 8, 12, 18, and 24 hours).

To assess block failure rate, defined as the requirement for more than one rescue morphine dose in the first postoperative hour.

To compare motor recovery (manual muscle test for quadriceps and iliopsoas, and active hip flexion range of motion) over the first 24 hours.

To compare time to first ambulation and length of hospital stay.

To compare intraoperative hemodynamic profiles (heart rate and mean arterial pressure).

To compare the incidence of block-related complications and morphine-related adverse events (e.g., nausea/vomiting, respiratory depression, hypotension, falls).

To compare block performance time and surgical duration between groups.

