## **9. Randomization, Allocation Concealment, and Blinding**

Randomization is based on a computer-generated sequence allocating patients to the three study groups in a 1:1:1 ratio. Allocation concealment is achieved using serially numbered, opaque, sealed envelopes prepared by a study coordinator not involved in patient care. Envelopes are opened only after induction of anesthesia. The anesthesiologist performing the block opens the envelope, prepares and administers the assigned intervention, and has no role in postoperative assessment. Patients, surgeons, ward staff, and outcome assessors are blinded to group assignment. Unblinding is permitted only if necessary for urgent clinical management, and the reason and timing are documented.

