### **11.5 Primary Outcome Analysis**

The primary outcome, total morphine consumption in the first 24 postoperative hours, will initially be assessed for normality. If the distribution is non-normal, the primary analysis will use the Kruskal–Wallis test to compare the three groups. If the overall test is significant ( $P < 0.05$ ), pairwise comparisons between groups (PENG vs AQLB, PENG vs Control, AQLB vs Control) will be conducted using Mann–Whitney U tests with

Bonferroni-adjusted significance thresholds. Median differences and 95% confidence intervals will be reported when appropriate.

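### The only masking of the puncture site is an optional sham dressing in Control at an unstated site, so the three arms can look different once patients wake

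*Combined protocol and SAP*

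**What the plan says.** Section 3 describes the trial as double-blind and names patients and outcome assessors as blinded. Section 9 goes further: "Patients, surgeons, ward staff, and outcome assessors are blinded to group assignment". The means given are envelopes opened after induction, blocks performed under general anesthesia, and a block operator who takes no part in assessing patients afterwards.

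The needle site itself is addressed once, for Control, in section 6.2.3: "A sham dressing may be applied to mimic a block site and maintain blinding".

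The two blocks are performed in different places. For PENG (6.2.1) the patient is supine and the probe is "positioned transversely over the anterior inferior iliac spine". For AQLB (6.2.2) the patient lies on the side, the probe is "placed horizontally above the iliac crest to visualize the transverse process", and the needle enters from behind. Neither section mentions a dressing over the puncture or a sham at the other site.

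The primary outcome in section 7.1 is the "cumulative dose of intravenous morphine administered in the PACU and on the ward up to 24 hours after surgery". Under section 6.4, "Rescue analgesia consists of morphine 0.05 mg/kg IV bolus when NRS" is 4 or more, at rest or on movement.

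**The concern.** The protocol itself treats the look of the block site as a blinding matter, because it gives the sham dressing that purpose. It then leaves the dressing to discretion and does not say where it goes. The safeguards in sections 3 and 9 protect allocation and the procedure. They do not cover what patients, ward staff and assessors can see after the patient wakes.

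The outcome is open to expectation. The patient's own score decides whether morphine is given, and staff obtain the score and give the drug. A patient or nurse who infers that no block was given may report or elicit more pain. That would bear on the comparisons with Control. The same route reaches the secondary NRS outcomes and block failure, which section 7.2 defines by rescue doses in the first postoperative hour.

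**Working it through.** The plan gives no figure on this point, so there is none to reproduce. The check sets the arm descriptions beside the blinding statements and asks which arms could be told apart by the site of a mark or dressing.

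**Inputs**
- PENG: puncture at the front of the hip (6.2.1).
- AQLB: puncture above the iliac crest, entered from behind (6.2.2).
- Control: no puncture; a dressing is allowed but not required, and its site is not stated (6.2.3).
- Planned comparisons: all three pairs of arms (11.5), two of which involve Control.

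**Scenarios.** Assume each block arm shows something at its own site, either a puncture mark or a dressing over it.

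| Dressing practice | Control vs PENG | Control vs AQLB | PENG vs AQLB | Pairs that can differ |
|---|---|---|---|---|
| Sham omitted in Control | can differ | can differ | can differ | 3 of 3 |
| One sham, PENG site | can match | can differ | can differ | 2 of 3 |
| One sham, AQLB site | can differ | can match | can differ | 2 of 3 |
| Identical dressings at both sites, all arms | match | match | match | 0 of 3 |

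The entries in the second and third rows are best cases. If real block sites are left undressed, a dressed Control patient matches neither block arm.

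The number of Control comparisons exposed is therefore 2 of 2 if the sham is omitted and at least 1 of 2 if a single sham is used. Because the wording is permissive, practice may also vary from patient to patient, so one trial could mix these rows.

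These are counts of pairs that can look different. They do not estimate how often anyone notices, or how much morphine use would change. The documents give nothing from which either could be calculated.

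**The case against.** **Visibility is not shown.** A 22-G puncture is small. Surgery is by an anterolateral approach (4.1), so the wound dressing may cover or adjoin the anterior site, and a patient may not easily see a posterior flank puncture. The documents settle neither point. This stands: the concern is that the arms can look different, not that they did.

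**Block sites are probably dressed.** A dressing meant to imitate a block site suggests that real ones carry a dressing. That is a natural reading, but it does not help: a Control patient without the optional sham would then be the one with nothing on the skin.

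**Staff have little discretion.** Rescue is a fixed weight-based bolus at a fixed pain threshold with a 24-hour maximum (6.4). This narrows the route through dosing decisions. The route through the patient's own report remains.

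**Dressings cannot do everything.** Surgeons may see the skin during preparation, and a block may reveal itself by sensory or motor effects. Both are true and limit what the fix achieves. Neither is a reason to leave an avoidable cue in place.

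A reader might infer more than the text supports:
- *That both Control comparisons are necessarily affected.* This is an upper limit, reached when the sham is omitted, or when a sham is used but real block sites are left undressed.
- *That the site is inspected at each of the 8 pain assessments.* Passive hip flexion need not expose a flank puncture, and the documents do not say who performs each test.
- *That PACU staff are unblinded because section 9 does not name them.* Those who score pain are reasonably covered as outcome assessors, and no dose-only PACU role is described. Naming them would be a minor clarification.

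**Conclusion.** The point holds as a weakness of design that is cheap to improve. The blinding asserted in sections 3 and 9 is backed, at the puncture site, only by an optional dressing in one arm at an unnamed location, while the two blocks use different locations. With no sham, Control can differ from both block arms. With one sham, it can match at most one, and the block arms can differ from each other in either case.

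The conclusion rests on one assumption that the documents neither confirm nor exclude: that a puncture or its dressing can be noticed by patients, ward staff or assessors. A reader might conclude that unblinding occurred or that the results favour the blocks. The documents do not support that, and the size of any bias cannot be computed from them. The visible difference between PENG and AQLB likewise does not establish a bias in that comparison.

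Separately, the statement that surgeons are blinded is stronger than the described procedures can secure. It has some consequence because the surgeon decides discharge (6.5), and so length of stay.

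**What to change.** In sections 6.2.1 to 6.2.3 and section 9, replace the permissive wording with a requirement along these lines:

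> Before leaving theatre, every patient in all three arms has identical opaque dressings at both the PENG site and the AQLB site on the operative side. They are applied by a team member who already knows the allocation and will not assess the patient after surgery. They stay in place until the 24-hour assessment unless lifted for a documented clinical reason.

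In section 9, qualify the claim about surgeons, and acknowledge that dressings do not conceal sensory or motor effects.

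**Cost.** Two small dressings per patient, or 93 × 2 = 186 at the target enrolment, and a few sentences of text. No needle is needed in Control. There are two modest downsides. The sites are slightly harder to inspect while block-related complications are being recorded (section 12), which is why documented lifting is allowed. A team member who knows the allocation must also be present at the end of surgery, although the blocks are given at the start of the case.

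**If enrolment is complete.** Section 11.8 uses the past tense about interim analyses, which suggests but does not prove that the trial has run. In that case, report which patients in each arm had dressings and where, and qualify the double-blind description accordingly.

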### **6.3 Intraoperative Analgesia and Monitoring**

Rescue analgesia consists of fentanyl 1 µg/kg IV if mean arterial pressure or heart rate increases more than 20% above baseline values. Hemodynamic variables (heart rate and mean arterial pressure) are recorded at baseline, 5 minutes after intubation, at skin incision, and then at regular intervals throughout surgery.

### **6.4 Postoperative Management**

In the post-anesthesia care unit (PACU), patients are monitored for 2 hours. NRS scores at rest and during movement, mean arterial pressure, and heart rate are recorded on arrival. On the ward, patients receive paracetamol 500 mg IV every 6 hours. Rescue analgesia consists of morphine 0.05 mg/kg IV bolus when NRS  $\geq 4$  at rest or during movement, with a maximum dose of 0.3 mg/kg in 24 hours. Ondansetron 0.1 mg/kg IV is administered for moderate or severe postoperative nausea/vomiting.

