## **1. Background and Rationale**

Total hip arthroplasty (THA) is widely performed for traumatic hip fractures and degenerative hip disease in older adults and is associated with substantial postoperative pain that can delay mobilization and prolong hospital stay. Effective multimodal analgesia is essential to facilitate early rehabilitation and reduce opioid-related adverse effects in this vulnerable population.

Opioid analgesics provide rapid pain relief but carry important risks in elderly patients, including respiratory depression, delirium, constipation, nausea/vomiting, and prolonged hospitalization. Regional anesthesia techniques, particularly peripheral nerve and fascial plane blocks, are increasingly used as opioid-sparing strategies after THA.

The pericapsular nerve group (PENG) block targets the articular branches of the femoral, obturator, and accessory obturator nerves supplying the anterior hip capsule via local anesthetic injection between the psoas tendon and superior pubic ramus. It has been described as providing effective, largely motor-sparing postoperative analgesia for hip surgery and acute pain after hip fracture.

The anterior quadratus lumborum block (AQLB) deposits local anesthetic in the fascial plane between the quadratus lumborum and psoas major muscles, aiming to block lumbar plexus articular branches and provide analgesia for hip surgery. Previous studies reported favorable analgesic profiles of AQLB in THA.

Both PENG and AQLB appear anatomically capable of covering the operative field in THA, but they may differ in their balance between analgesic efficacy, opioid-sparing effect, and motor impairment. Comparative data between these two techniques in elderly

patients undergoing THA under general anesthesia are limited. This trial evaluates whether ultrasound-guided PENG block or AQLB offers superior postoperative analgesia and functional recovery compared with standard opioid-based analgesia and compares PENG and AQLB directly.

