## **11.6 Secondary Outcome Analyses**

Total intraoperative fentanyl dose and other continuous secondary outcomes (such as time to first rescue morphine, time to ambulation, length of hospital stay, block performance time, and surgical duration) will be analyzed using one-way ANOVA for normally distributed data or Kruskal–Wallis test for skewed data, with appropriate pairwise post-hoc tests. NRS pain scores at rest and during movement and motor recovery scores will be analyzed at each time point using Kruskal–Wallis tests with Bonferroni-adjusted Mann–Whitney comparisons. Exploratory repeated-measures analyses (e.g., mixed-effects models) may be used to evaluate time-by-group interactions when assumptions are satisfied. Categorical outcomes, such as adverse event incidence and block failure rates, will be compared using chi-square or Fisher’s exact tests as appropriate.

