## **12. Safety Monitoring**

All serious adverse events and suspected block-related complications will be recorded from block performance until 24 hours postoperatively and throughout the hospital stay. Any severe or unexpected serious adverse event judged related to the intervention will be reported to the institutional ethics committee according to local regulations. Given the limited size and low risk of the study, no independent data monitoring committee is established; safety monitoring responsibilities lie with the principal investigator and the department head.

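### Respiratory depression and hypotension are compared between arms without a definition or a common postoperative recording schedule, so ascertainment rests on unspecified routine observation

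*Combined protocol and SAP*

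**What the plan says.** Section 7.2, repeating Section 2.2, makes the incidence of block-related complications and "morphine-related adverse events (e.g., nausea/vomiting, respiratory depression, hypotension, falls") a secondary outcome compared between groups. Section 11.6 supplies the test: "Categorical outcomes, such as adverse event incidence and block failure rates, will be compared using chi-square" or Fisher's exact test. Section 1 places respiratory depression first among the reasons for sparing opioids in this population, stating that they "carry important risks in elderly patients, including respiratory depression, delirium, constipation, nausea/vomiting, and prolonged hospitalization".

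On measurement after surgery, Section 6.4 says that in the PACU "patients are monitored for 2 hours" and that "NRS scores at rest and during movement, mean arterial pressure, and heart rate are recorded on arrival". It does not list what is monitored during those 2 hours, how often, or what is transcribed. Oximetry appears only in the anesthesia regimen of Section 6.1 ("Monitoring includes ECG, non-invasive blood pressure, pulse oximetry"). The eight common postoperative time points in Section 7.2 ("30 min, 2, 4, 6, 8, 12, 18, and 24 hours") are given for pain scores only.

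On event capture, Section 12 begins: "All serious adverse events and suspected block-related complications will be recorded". It gives no rule for non-serious morphine-related events. Section 10 names PACU and ward observation charts as source documents without stating their content or frequency. Section 9 blinds ward staff and outcome assessors.

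**The concern.** An incidence can be compared between arms only if the event means the same thing, and is looked for equally hard, in each arm. The plan defines block failure (Section 7.2) and first walk (Section 6.5), but not respiratory depression or hypotension. Section 6.1 mentions treating hypotension without saying what counts as hypotension.

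The plan schedules measurements carefully elsewhere: hemodynamics during surgery (Section 6.3) and pain at eight times afterwards. The gap falls in the 24 hours when rescue morphine may be given. Rescue is triggered by pain, and pain is what the blocks are meant to change. If an event tends to be noticed when someone comes to give a bolus, an arm with more boluses has more chances of a recorded event at the same true risk. What is at stake is the reading of a secondary safety comparison that bears on the rationale for opioid sparing.

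**Working it through.** The plan states no figure on this point, so there is nothing to reproduce. The check has two parts: a comparison of the text, then an illustration of how large unequal detection could be.

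**Text, side by side**

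- Compared events: respiratory depression and hypotension (Sections 2.2, 7.2), tested under Section 11.6.
- Definitions: none in any section.
- Postoperative blood pressure: one stated recording time, PACU arrival (Section 6.4).
- Postoperative respiratory rate, oxygen saturation, sedation: no stated recording time.
- Observation common to all arms: 2 hours of PACU monitoring with unlisted variables (Section 6.4), and eight pain assessments with no vital signs attached (Section 7.2).
- Remaining period: 24 − 2 = 22 hours on the ward, covered by charts of unstated content and frequency (Section 10).
- Capture rule: serious events and suspected block-related complications (Section 12).

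**Illustration**

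Inputs from the plan: a rescue bolus of 0.05 mg/kg and a 24-hour ceiling of 0.3 mg/kg (Section 6.4), so at most 0.3 / 0.05 = 6 boluses per patient; 8 common pain visits (Section 7.2); 31 patients per arm (Section 8).

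Assumptions, not in the plan: equal true risk in both arms; 2 rescue contacts in a block arm and 6 in Control; each contact independently detects an event with probability d, from 0.1 to 0.5.

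Formula: recorded rate = true risk × [1 − (1 − d)^c], where c is the number of contacts. The true risk cancels in the ratio of the arms.

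(a) Events noticed only at rescue contacts: c = 2 versus 6.
(b) The eight common visits also detect events: c = 2 + 8 = 10 versus 6 + 8 = 14.

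| d | (a) block | (a) Control | ratio | (b) block | (b) Control | ratio |
|---|---|---|---|---|---|---|
| 0.1 | 0.190 | 0.469 | 2.47 | 0.651 | 0.771 | 1.18 |
| 0.2 | 0.360 | 0.738 | 2.05 | 0.893 | 0.956 | 1.07 |
| 0.3 | 0.510 | 0.882 | 1.73 | 0.972 | 0.993 | 1.02 |
| 0.5 | 0.750 | 0.984 | 1.31 | 0.999 | 1.000 | 1.00 |

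Entries are proportions of true events recorded. For example, at d = 0.3 in (a): 1 − 0.7² = 0.510, 1 − 0.7⁶ = 0.882, and 0.882 / 0.510 = 1.73.

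In patients, with an assumed true risk of 10% and d = 0.3: (a) 31 × 0.10 × 0.510 = 1.6 recorded in a block arm against 31 × 0.10 × 0.882 = 2.7 in Control; (b) 3.0 against 3.1.

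The possible distortion therefore runs from material to negligible. What separates the two cases is whether the common visits look for these events, and the plan does not say.

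**The case against.** A reader might infer two stronger things, and the documents support neither.

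The first is that no respiratory variable is recorded after surgery. Silence about a schedule is not evidence that nothing is recorded. Every patient is monitored for 2 hours in the PACU, observation charts are source documents, and Section 10 refers to pre-designed case report forms that are not part of the documents. The supportable statement is that no postoperative recording time is stated. Likewise, Section 12 governs safety recording and reporting; its narrower scope does not prove that outcomes listed in Section 7.2 go uncollected.

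The second is that detection is driven by how often staff attend each arm, so that neither a difference nor its absence can be interpreted. That is an inference. All arms share the PACU period and the eight pain visits, and ward staff and assessors are blinded. Some boluses may be given at a scheduled pain visit and add no separate contact. Nothing in the documents says that chart frequency rises with morphine doses. Under case (b) the bias nearly disappears.

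It is also fair to say that Section 7.2 does not confine hypotension to the postoperative period and that Section 6.3 records pressure at regular intervals during surgery; that these events are two examples within one of many secondary objectives; and that even case (a) above amounts to about one patient per arm.

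What survives is this. Blinding removes bias from knowing the arm, but it does not equalise contacts that follow pain. PACU monitoring covers 2 of the 24 hours, with variables unstated. Charts of unknown content and frequency do not ensure equal ascertainment. The common visits protect the comparison only if the relevant variables are recorded at them, and the plan does not attach those variables to them.

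**Conclusion.** The point holds as a gap in outcome definition and scheduled measurement. Two compared outcomes have no definition and, after surgery, no stated measurement common to all arms beyond a single arterial pressure on PACU arrival. Differential detection between arms is plausible but not demonstrated. Its illustrated size spans a Control-to-block ratio of 2.47 down to 1.00, resting on the assumed contact numbers, equal true risk and 10–50% detection per contact. The change is worth making because it is cheap and moves the trial towards the favorable end of that range. It affects one secondary safety comparison and leaves the primary outcome untouched.

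**What to change.** At each of the eight existing pain time points, have the same blinded assessor record respiratory rate, oxygen saturation, a sedation score and mean arterial pressure in every arm. Fix one numerical outcome definition of respiratory depression and one of hypotension before unblinding. Base the between-arm comparison on these scheduled readings, and list events found between visits separately by arm.

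If data collection is already complete, fix the definitions before unblinding, extract the chart readings nearest the eight times, report the number of readings available per arm, and label the comparison descriptive.

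The cost is four added fields on an existing form, 4 × 8 = 32 readings per patient, and a little assessor time at visits that already take place. No extra visits are needed. The change concerns data recording and outcome definition only and proposes no treatment threshold.
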